9.1.1 Discontinuation of study treatment

Discontinuation of study treatment for a subject occurs when study treatment is stopped earlier than the protocol planned duration and can be initiated by either the subject or the investigator.

The investigator must discontinue study treatment for a given patient if, he/she believes that continuation would negatively impact the subject's well-being.

Study treatment must be discontinued under the following circumstances:

- Subject decision
- Pregnancy (see [Section 8.4.2](#) and [Section 10.1.4](#))
- Use of prohibited treatment (see [Section 6.2.2](#))
- Any situation in which continuation with study treatment might result in a safety risk to the subject
- Unsatisfactory therapeutic effect, e.g. a subject requires injections more frequently than every 8 weeks after the loading phase (week 8, loading arm) or baseline (non-loading arm).
- Subjects develop intraocular inflammation, retinal vasculitis and/or retinal vascular occlusion

If discontinuation of study treatment occurs, the investigator should make a reasonable effort to understand the primary reason for the subject's premature discontinuation of study treatment and record this information on the appropriate eCRF page.

Subjects who prematurely discontinue study treatment for any reason, except for withdrawal of consent (refer to [Section 9.1.2](#)), should continue in the study with all the scheduled visits and assessments (except disease stability assessment, administration of study treatment, post-injection assessment and adherence to prohibited medication list) until EOS. These patients can be switched to standard of care anti-VEGF IVT as per investigator's discretion. Any IVT injection is contraindicated in subjects with active intraocular or periocular infections and in subjects with active intraocular inflammation; therefore, the investigators must verify that these conditions are not present in the study eye prior to every injection.

Subjects who decide not to participate in the study further should NOT be considered withdrawn from the study, UNLESS they withdraw their consent (see [Section 9.1.2](#)). **Where possible, subjects should return for the EOS visit assessments to be performed as scheduled in Table 8-1.**

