In the “loading arm”, patients will receive three consecutive injections every 4 weeks at baseline, weeks 4 and 8, which should be at least 21 days apart, followed by an injection every 12 weeks. In the “non-loading arm”, patients will receive one initial injection followed by an injection every 12 weeks. For both study arms the assessment of disease activity will be performed 8 and 12 weeks after the previous injection. If disease activity is identified by the investigator for the first time at any visit after / from week 8 respectively, patients should stay on a q12w dosing, if the decline in BCVA is clinically non-significant (BCVA loss < 4 ETDRS letters) compared to the previous visit. If after / from week 8 BCVA-loss of ≥ 5 ETDRS letters appears compared to the previous visit or disease activity is identified for a second time based on the investigator’s judgment of visual and / or anatomic outcomes and signs of disease activity, patients must be assigned to q8w dosing. One attempt of interval re-extension from q8w to q12w treatment will be allowed based on the investigator’s judgement if no disease activity (DA) is detected during the subsequent visit(s). If the patient shows significant DA at any visit after the re-extension attempt, injection intervals will be fixed to q8w until the end of the study.

Patients who require injections more frequently than every 8 weeks after the loading phase (week 8, loading arm) or baseline (non-loading arm) will be discontinued from further study treatment.

3. Post-treatment follow-up period: Week 48 to week 52

For all patients, the last study assessment will be performed at week 52.

Patients withdrawn from the study prior to study completion will be asked to return for an early discontinuation visit (EOS / Visit 14), four weeks (± 7 days) following their last study visit.

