2.3 Patient disposition, demographics and other baseline characteristics

2.3.1 Patient disposition

Using all enrolled patients the number of patients screened, randomized, discontinued prematurely and completed treatment/ study by center and treatment will be displayed. For patients who discontinued/ completed treatment/ study percentages are computed using the number of randomized patients.

Furthermore, a listing will be provided for first patient first visit and last patient last visit by center.

In addition, the frequency of patients who completed/ discontinued is displayed separately for screening phase (all enrolled patients), for treatment completion (Randomized Set) and for study completion (Randomized Set) and the reason for discontinuation is analysed according to CRF-given categories.

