2.7.2 Statistical hypothesis, model, and method of analysis

Secondary endpoints will be analyzed using adequate descriptive statistics, if not otherwise specified. Details on planned analyses are listed in the table below.

Table 2 Endpoints and statistical method

Endpoints for secondary objectives	Statistical method
1.Treatment interval	
1.1. Mean treatment interval (overall as well as per study group comparing treatment intervals from week 8 to week 52 in the study vs. 24 weeks to baseline prior to enrollment)	Descriptive analysis of injection intervals (weeks): Summary statistics (n,mean, SD, min, median, max) for - Mean treatment interval from week 8 to week 52 - Mean treatment interval within 24 weeks prior to baseline. - Last treatment interval under observation Box Plot for “last treatment interval under observation”. Stacked Bar Chart for patients on q8w and q12w by visit (last documented DAA).

1.2. Rate of patients (overall and per group) with prolonged interval compared to mean treatment interval in last 24 weeks to baseline prior to enrollment

- **Frequencies and percentages (n(%))** for total FAS and both treatment arms.

- **Logistic regression model**

Dependent variable: interval prolongation* (Y/N)

Factors:

- treatment arm
- baseline BCVA
- age

Odds-ratio, 95% CI and p-value.

Estimates for , non-loading arm, loading arm and difference (non-loading – loading).

* Prolongation is calculated by comparing the “mean treatment interval in last 24 weeks prior to first brolucizumab injection” (defined in section 2.3.2) with the time interval between the last two brolucizumab injections. Patients with only one injection in treatment period are calculated as non-responders (no interval prolongation).

2. Maintenance of q12w intervals

2.1. Comparison of proportions of patients maintained at a q12w interval at week 52 between the two arms

- **Frequencies and percentages (n(%))** for total FAS and both treatment arms.

- **Logistic regression model**

Dependent variable: “q12w” (Yes/No): “DAA maintained at q12w from baseline / upload to week 52”

Factors:

- treatment arm
- baseline BCVA
- age

Odds-ratio with 95% CI and p-value.

Patients who discontinued treatment prior to week 52 are calculated as non-responders.

2.2. Distributions of patients at q8w/q12w intervals from baseline to week 52

Descriptive statistics for treatment regimens:
Frequencies and percentages (n (%)) by visit

3. Functional Outcomes

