5.4 Statistical models

5.4.1 Primary analysis

1) SAS-Code for **mixed model for repeated measures (MMRM)**:

Estimates for the primary objective ("Mean change in BCVA from baseline to mean of visits at week 40 to week 52 (Visit 11 to 14)") and the secondary objective ("Mean change in BCVA from baseline to mean of visits at week 16 to week 28 (Visit 5 to 8)") in one single model:

```
proc mixed alpha=0.1;
  where fasfl=Y and trteyen=1;
  where 2 le avisitn le 14;
  class subjid trtan avisitn;
  model chg = base age trtan avisitn trtan*avisitn /ddfm=kr;
  repeated avisitn / sub = subjid type = un;
  lsmeans trtan*avisitn /slice = avisitn cl ;
  estimate 'Treatment difference averaged over week 40 to week 52'
    trtan -1 1
    trtan * avisitn
      0 0 0 0 0 0 0 0 -0.25 -0.25 -0.25 -0.25
      0 0 0 0 0 0 0 0 0.25 0.25 0.25 0.25/cl;
  estimate 'Treatment difference averaged over week 16 to week 28'
    trtan -1 1
    trtan * avisitn
      0 0 0 -0.25 -0.25 -0.25 -0.25 0 0 0 0 0 0
      0 0 0 0.25 0.25 0.25 0.25 0 0 0 0 0 0/cl;
run;
```

3) SAS-Code for **logistic regression** model:

- Secondary endpoint: "rate of patients (overall and per treatment arm) with prolonged interval (*intlong*) compared to mean treatment interval in last 24 weeks prior to enrollment"

```
proc logistic descending alpha=0.05;
  where fasfl=Y;
  class trtan;
  model intlong = base age trtan;
run;
```

- Secondary endpoint: "proportions of patients maintained at a q12w interval from baseline / upload to week 52"

```
proc logistic descending alpha=0.05;
  where fasfl=Y;
  class trtan;
  model q12w = base age trtan;
run;
```

where 'maintained at a q12w interval' (q12w = Yes) is defined as DAA = q12w in all visits AND no treatment discontinuation.

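### Endpoint 1.1 drops the non-loading arm's first interval under a window change that SAP section 4 does not list, and endpoint 1.2 can score a stop for lack of efficacy as a prolonged interval

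*SAP*

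**What the plan says.** **Endpoint 1.1 (mean treatment interval).** Protocol Table 2-1 sets the on-study window as baseline to week 52. SAP Table 1.1, section 2.1.1 and Table 2 in section 2.7.2 all use week 8 to week 52. The SAP formula takes the last injection minus the first one at week 8 or later, divided by the number of injections from week 8 less one. SAP section 4, which records departures from the protocol, lists only the rewording of the q12w-maintenance endpoint.

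**Endpoint 1.2 (rate with prolonged interval).** SAP Table 2 compares the pre-study mean interval "with the time interval between the last two brolucizumab injections". The only scoring rule for early stops is that patients with a single injection are non-responders. Section 2.7.3 adds only that missing values are not replaced.

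**The neighbouring endpoint.** For q12w maintenance (2.1), the same table says "Patients who discontinued treatment prior to week 52 are calculated as non-responders", and section 5.4.1 repeats this: being maintained "is defined as DAA = q12w in all visits AND no treatment discontinuation".

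**Who must stop.** SAP 1.1 takes off study treatment "Patients who require injections more frequently than every 8 weeks after the loading phase" (or after baseline in the non-loading arm). Protocol 9.1.1 gives the same case as an example of treatment failure: "Unsatisfactory therapeutic effect, e.g. a subject requires injections more frequently than every 8 weeks after the loading phase".

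**The concern.** Interval prolongation is the first-listed secondary objective, and endpoint 1.2 is reported with an odds ratio, confidence interval and p-value.

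For endpoint 1.2, the rule looks only at gaps closed by a second brolucizumab injection. Under SAP 1.1, "the assessment of disease activity will be performed 8 and 12 weeks after the previous injection", so failure to hold an interval is found after the last injection. If the patient is then taken off treatment, the interval that failed never becomes a gap between two study injections. The score rests on the gap before it, and a patient removed because 8 weeks could not be held may be reported as a success. In the loading arm, the gap used may be one that the initiation regimen fixed, which says nothing about durability.

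For endpoint 1.1, the result depends on which document is followed. The SAP version treats the arms unequally: in the loading arm it removes only initiation gaps, but in the non-loading arm it removes an interval that the protocol (sections 6.7.2 and 8) counts as part of the q12w/q8w phase.

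**Working it through.** The documents state no figure for either endpoint, so there is none to reproduce. Inputs are the nominal schedules in Protocol 3 and 6.7.2, the eligible pre-study interval of 26 to 86 days (Protocol 5.1), the SAP 2.1.1 formula, and 25 or 23 patients per group (SAP section 3).

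**Endpoint 1.1.** Mean = (last injection - first injection in window) / (injections in window - 1), in weeks.

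| Injections at week | SAP window (from week 8) | Protocol window (from baseline) |
|---|---|---|
| Loading, q12w: 0, 4, 8, 20, 32, 44 | 36/3 = 12.0 | 44/5 = 8.8 |
| Loading, q8w: 0, 4, 8, 16, 24, 32, 40, 48 | 40/5 = 8.0 | 48/7 = 6.9 |
| Non-loading, q12w: 0, 12, 24, 36, 48 | 36/3 = 12.0 | 48/4 = 12.0 |
| Non-loading, q8w: 0, 8, 16, 24, 32, 40, 48 | 40/5 = 8.0 | 48/6 = 8.0 |
| Non-loading: 0, 12, 20, 28, 36, 44 | 32/4 = 8.0 | 44/5 = 8.8 |
| Non-loading: 0, 8, 16, 28, 40 | 32/3 = 10.7 | 40/4 = 10.0 |
| Non-loading: 0, 8, 20, 32, 44 | 36/3 = 12.0 | 44/4 = 11.0 |
| Non-loading, stopped: 0, 12 | 0/0, no value | 12/1 = 12.0 |

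For the non-loading arm I enumerated every path to week 48 made of 12-week gaps, then 8-week gaps, one re-extension to 12, then 8 again (20 paths). The SAP mean minus the baseline-window mean runs from -0.8 (8.0 against 8.8) to +1.0 (12.0 against 11.0). The upper end needs re-extension directly after a switch at week 8. If at least two 8-week intervals come before any re-extension (14 paths), it is +0.7 (10.7 against 10.0).

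Counting each arm from its last initiation injection uses the middle column for the loading arm and the right-hand column for the non-loading arm. On q12w this gives 12.0 in both arms.

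**Endpoint 1.2, stop for lack of efficacy.** Take a patient on q8w with a pre-study mean of 6 weeks, stopped at week 20 for needing shorter intervals. Injections are 0, 4, 8, 16 (loading) or 0, 8, 16 (non-loading). The last gap is 8 weeks in both, and 8 > 6, so the score is prolonged. The same happens for any mean under 8 weeks, or under 12 weeks if the last completed gap was 12.

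**Endpoint 1.2, initiation gap.** A q12w patient stops after week 12 and before any week 20 injection.

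- Loading (0, 4, 8): last gap 28 days. This is not prolonged for means of 28 days or more, but prolonged for means of 26 or 27 days, on the evidence of a loading gap alone.
- Non-loading (0, 12): last gap 84 days, so prolonged for means up to 83 days.
- The arms therefore score oppositely for means of 28 to 83 days. Once the loading arm has its week 20 injection, both last gaps are 12 weeks and the scores agree.

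These figures are for nominal timing. With 7-day visit windows and injection up to 3 days after the visit, the loading gap from week 4 to week 8 is at most (56 + 7 + 3) - (28 - 7) = 45 days. Protocol 6.7.2 can be read as allowing the baseline injection up to 7 days late, which makes the non-loading first gap at least (84 - 7) - 7 = 70 days. On that reading the opposite scoring is certain only for means of 45 to 69 days.

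**Leverage.** One patient moves an arm's rate by 1/25 = 4.0 points, or 1/23 = 4.3 points.

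**The case against.** Endpoint 1.2 can be defended as an on-treatment measure of the interval achieved. Endpoint 2.1 asks whether q12w was held to week 52, so failing discontinuations there does not oblige 1.2 to do the same, and a patient who went from about 4 weeks to 6 or 7 has in a sense been prolonged. That justifies not failing every discontinuation in the main analysis. It does not justify counting as prolonged a patient stopped because the credited interval could not be held.

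A reader might infer that the opposite scoring of early stops is a bias made by the SAP and cured by better counting. The documents do not support this. The non-loading patient has completed 12 weeks, and the loading arm cannot complete a 12-week maintenance interval before week 20. The contrast is largely real, and for stops unrelated to efficacy the recommended main analysis leaves it unchanged for means of 28 to 83 days.

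Nor does the 0/0 patient vanish. The same cell of Table 2 plans a summary and box plot of the last interval observed, where that patient contributes 12 weeks. The formula also fails for a loading patient stopped after week 8, but that patient has no completed maintenance interval to lose.

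The SAP states the week-8 window openly in three places, and it helps the loading arm, so it would be wrong to call the window itself a mistake. What remains is that it is missing from section 4 and that it discards a genuine interval in one arm only.

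Finally, scoring by reason for stopping relies on reasons recorded by open-label investigators. SAP 2.3.1 says only that "the reason for discontinuation is analysed according to CRF-given categories", and the categories are not shown. Protocol 6.2.3 sends lack of efficacy needing prohibited treatment to discontinuation, and 9.1.1 lists prohibited treatment as its own reason. A rule tied to one category would miss such patients. This objection stands and shapes the fix.

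**Conclusion.** The point holds on the text and the arithmetic. Endpoint 1.1 departs from the protocol without an entry in section 4 and shifts non-loading patient means by -0.8 to +1.0 week when the interval changes, zero otherwise. Endpoint 1.2 can report as prolonged a patient withdrawn because 8 weeks could not be held, and can use a 4-week initiation gap as the on-study interval.

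The effect on an arm's rate is about 4 points per affected patient. The documents do not say how many there will be, so no total bias can be claimed. Listings of injections (SAP 2.4.1) and tables of discontinuation reasons would let a reader find these patients, but the rate, odds ratio and p-value would not separate them.

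The figures assume nominal schedules unless stated. These are secondary, descriptive endpoints in about 50 patients, so this is a change that should be made, of modest severity.

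**What to change.** 1. For both endpoints, count on-study intervals from the last initiation injection: baseline in the non-loading arm, week 8 in the loading arm. List this in SAP section 4 as a departure from the protocol's baseline window.
2. For endpoint 1.2, score as not prolonged any patient with no completed post-initiation interval, and any patient who stops study treatment for lack of efficacy. Include those stopped to receive other anti-VEGF treatment in the study eye for lack of efficacy, whichever category was ticked.
3. Add a supplementary analysis of 1.2 that scores all treatment discontinuations as not prolonged. It does not depend on recorded reasons and is the only version that removes the early-stop difference between arms. State in the SAP that the main analysis retains that difference for stops unrelated to efficacy.

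The cost is SAP wording, derivation code and one extra table; injection dates, discontinuation reasons and other treatments are already collected. The reported rate will be somewhat lower, and the main analysis depends in part on recorded reasons. Some patients who need under 8 weeks but longer than before the study will be scored not prolonged. The supplementary analysis also fails patients who stop for reasons such as inflammation or pregnancy after several 12-week intervals, so it should not be the main analysis.

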6.5 Dose escalation and dose modification

No study treatment dose modification is allowed.

Deviations from dose intervals during the initiation phase and/or dose adjustments during the whole study are not allowed.

Interruption of study treatment is allowed if warranted by an AE.

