6.6 Additional treatment guidance

6.6.1 Treatment compliance

The date and time of all study treatment injections administered during the study and any deviations from the protocol treatment schedule will be captured by the investigator staff or by the field monitor on the appropriate study treatment dispensing form.

Exposure to the study treatment will be based on the number of injections administered. Compliance with the study treatment will be assessed by the field monitor at each visit using medication counts and information provided by the investigator / study personnel.

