A \pm 7-day visit window is allowed, except for baseline/day1 and the week 52 visit (\pm 21-day visit window), should the subject be unable to return per scheduled visit. For a given protocol visit, assessments can be performed on two consecutive days in which both days must occur within the \pm 7-day visit window.

Treatment is intended to be administered on the day of study visit, or if this is not possible, within 3 days after the study visit at which the per-protocol assessments took place. For all visits, efficacy assessments ([Section 8.3](#)) and safety assessments ([Section 8.4](#)) should be performed prior to any administration of study treatment.

Missed or rescheduled visits should not lead to automatic discontinuation. Subjects who prematurely discontinue the study for any reason should be scheduled for a visit as soon as possible, at which time all of the assessments listed for the final visit will be performed. At this final visit, all dispensed investigational product should be reconciled, and the adverse event and concomitant medications recorded on the CRF.

If the COVID-19 pandemic limits or prevents on-site study visits, study treatment could not be administered and other study assessments may not be performed. Alternative methods of safety monitoring may be implemented. Depending on local regulations, site capabilities and patient’s visit status in the study, phone calls or virtual contacts (e.g. teleconsult) can be performed for safety follow-up for the duration of the pandemic, until it is safe for the participant to visit the site again.

Table 8-1 Assessment schedule

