2.1.1 General definitions

The term study treatment is used for Brolucizumab 6 mg/0.05 mL.

The baseline visit is defined as day 1/visit 1.

The on-treatment period lasts from the date of first administration of study treatment to 30 days after the last administration of study treatment (EOT) or EOS whichever is the latest.

Calculation of treatment interval:

- “Mean treatment interval from week 8 to week 52”: (last injection – first injection from week 8 on*) divided by (number of injections from week 8 to week 52 -1)

*the first injection from week 8 on could be at week 8 or later.

- “Mean treatment interval in last 24 weeks prior to first brolucizumab injection” will be calculated as: (date of first brolucizumab injection - date of first anti-VEGF pre-treatment within last 24 weeks) divided by number of injections within 24 weeks prior to first brolucizumab injection.

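### The interval endpoints use raw dates of injections given, so a missed or late dose lengthens the computed interval and, in one position, can turn a patient from not prolonged to prolonged

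*SAP*

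**What the plan says.** SAP 2.1.1 defines the in-study mean interval as "last injection – first injection from week 8 on*) divided by (number of injections from week 8 to week 52 -1", in other words elapsed time over the number of gaps between injections actually given. The pre-study comparator also comes from dates: time from the first anti-VEGF injection in the 24-week window to the first brolucizumab injection, "divided by number of injections within 24 weeks prior to first brolucizumab injection".

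SAP 2.7.2, Table 2, summarises under endpoint 1.1 both means and the last interval observed, with a box plot of the latter. Endpoint 1.2 decides prolongation by comparing the pre-study mean "with the time interval between the last two brolucizumab injections". The one stated exception is: "Patients with only one injection in treatment period are calculated as non-responders (no interval prolongation". Endpoint 1.2 also has a logistic model with odds ratio, confidence interval and p-value.

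No other SAP rule deals with an injection that was due and not given. Section 2.7.3 replaces no missing secondary values, 5.1.1 covers only an unknown injection date, 5.5 excludes nobody for missed doses, and no sensitivity analysis is planned.

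The protocol foresees such gaps in patients who stay on treatment. Section 6.5: "Interruption of study treatment is allowed if warranted by an AE". Section 8: "Missed or rescheduled visits should not lead to automatic discontinuation". Sections 8 and 8.4 expect visits without treatment because of COVID-19, and 6.7.2 provides for cancelling an injection over a safety concern. The data to identify these gaps exist, since under 6.6.1 "any deviations from the protocol treatment schedule will be captured by the investigator staff".

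**The concern.** The objective is to learn whether patients can be treated at longer intervals than before. In this regimen the interval is set to 8 or 12 weeks by disease activity, so a long interval is informative when it follows from quiet disease. A gap that is long because a due dose was not given says nothing about durability, yet both formulas count it in the favourable direction.

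The SAP is also inconsistent with itself here. The stacked bar chart under 1.1 uses the last documented DAA, and endpoint 2.1 uses the DAA with treatment discontinuation as failure. The same patient could appear as q8w in the chart and at 16 weeks in the box plot of the same endpoint. At stake is whether some under-treatment is reported as interval prolongation.

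**Working it through.** **Inputs.** Planned intervals of 8 or 12 weeks after initiation (Protocol 3 and 6.7.2); eligible pre-study intervals of 26 to 86 days (Protocol 5.1, criterion 5), where 86/7 = 12.3 weeks; about 25 patients per arm (SAP 3). The plan gives no expected interval and no rate of missed injections.

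**Formulas.** Mean = (last − first injection from week 8 on) / (number − 1). Last gap = difference between the last two injections given. Prolonged is read as a last gap strictly longer than the pre-study mean. The planned schedules come first in each block. The q8w rows assume the earliest possible move to q8w.

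| Case | Injections from week 8 | Mean (weeks) | Last gap (weeks) |
|---|---|---|---|
| Loading, q8w as planned | 8, 16, 24, 32, 40, 48 | 40/5 = 8.0 | 8 |
| week 24 missed | 8, 16, 32, 40, 48 | 40/4 = 10.0 | 8 |
| week 40 missed | 8, 16, 24, 32, 48 | 40/4 = 10.0 | 16 |
| week 40 given at week 44, then no more | 8, 16, 24, 32, 44 | 36/4 = 9.0 | 12 |
| week 48 missed | 8, 16, 24, 32, 40 | 32/4 = 8.0 | 8 |
| Loading, q12w as planned | 8, 20, 32, 44 | 36/3 = 12.0 | 12 |
| week 20 missed | 8, 32, 44 | 36/2 = 18.0 | 12 |
| week 32 missed | 8, 20, 44 | 36/2 = 18.0 | 24 |
| Non-loading, q12w as planned | 12, 24, 36, 48 | 36/3 = 12.0 | 12 |
| week 36 missed | 12, 24, 48 | 36/2 = 18.0 | 24 |

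**Endpoint 1.1.** Any interior miss raises the mean: 8.0 to 10.0 weeks on q8w, 12.0 to 18.0 on q12w. Missing the final planned dose leaves it unchanged.

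**Endpoint 1.2.** Two conditions must both hold.

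- The affected dose lies between the last two injections given. With week 24 missed the last gap is still 8 weeks; with week 40 missed it is 16.
- The prior mean is at or above the assigned interval. A q8w patient with a prior mean of 6 weeks is prolonged on the planned schedule anyway (8 > 6). With a prior mean of 8 the patient goes from not prolonged (8 vs 8) to prolonged (16 vs 8). A gap of 16 or 24 weeks exceeds the 12.3-week entry limit, so the result is then prolonged for any eligible prior interval. In the late-dose case (last gap 12) the label changes for prior means from 8 to under 12 weeks. On q12w it can change only for prior means of 12 to 12.3 weeks.

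**Size per patient.** 1/25 = 4.0 points in an arm of 25, and 1/50 = 2.0 points overall.

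**Frequency, assumption only.** With a miss probability r per injection of 2% to 10%, the one dose relevant to 1.2 is missed in about 2% to 10% of q8w patients. If half of an arm of 25 were on q8w, that is 12.5 × 0.02 = 0.25 to 12.5 × 0.10 = 1.25 patients per arm, before restricting to prior means of 8 weeks or more. The chance of missing at least one of the four interior q8w doses is 1 − (1 − r)^4 = 7.8%, 18.5% and 34.4% for r = 2%, 5% and 10%. That second figure bears on the 1.1 mean only.

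**The case against.** The strongest defence is that the interval a patient actually received is a legitimate quantity. Protocol Table 2-1 speaks of the treatment interval, not the assigned one, and raw dates are used on both sides, so missed injections before the study lengthen the comparator too. Replacing only the in-study gaps would compare an assigned interval with an actual one and lean against prolongation. The plan also reports the assigned regimen elsewhere (bar chart, endpoints 2.1 and 2.2), lists all injections, summarises regimen switches, and has deviations assessed before database lock.

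Much of this stands. It is a good reason to keep the raw-date version and not overwrite it. It does not remove the point. Eligibility holds the pre-study intervals to 26 to 86 days, while nothing caps an in-study gap. Nothing in the planned output tells the reader which long gaps contain an omitted dose, and the odds ratio and p-value for 1.2 rest on the raw gap alone.

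A reader might infer more than the documents support:

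- *Every missed q8w dose is scored as a 12- or 16-week interval, or 8–34% of q8w patients are misclassified.* Position and prior mean limit endpoint 1.2, and the larger percentages concern the 1.1 mean at assumed rates.
- *Every foreseen reason for delay produces such a gap.* Under Protocol 6.2.1.1 cataract surgery needs at least 7 days after the previous dose and 14 before the next, 21 days together, which fits within 8 weeks. No duration is given for IOP to normalise (8.4.3). Intraocular inflammation, retinal vasculitis and retinal vascular occlusion lead to discontinuation of study treatment (9.1.1), so no later injection closes a long gap.
- *The comparison between arms is biased.* Nothing in the documents suggests that missed doses would differ by arm.

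**Conclusion.** The point holds in limited form. The 1.1 summary statistics, the last-interval summary and endpoint 1.2 cannot tell an interval extended for quiet disease from one lengthened by a missed, interrupted or late dose, and any such error runs towards longer intervals. For 1.2 it matters only when the dose lies between the last two injections given and the prior mean is at or above the assigned interval; in practice this means mainly q8w patients with a prior mean of 8 weeks or more. Each such patient is worth 4 points in an arm of 25.

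How many there will be is unknown; the 2–10% range is an assumption. The statement that a 16-week gap is prolonged for any eligible patient takes the 86-day limit as covering all pre-study intervals, including the last one before baseline. Severity is minor to moderate: the endpoints are secondary and descriptive, and the DAA-based outputs already show part of the picture.

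**What to change.** In SAP 2.1.1 and Table 2:

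1. From the dose administration record and the DAA, flag each in-study gap that contains a scheduled injection that was missed, interrupted or given outside its window, judged against the q8w or q12w interval in force when that injection fell due.
2. Report the number of flagged gaps per arm.
3. Report 1.1 (mean and last interval) and 1.2 (rates and logistic model) a second time, using the DAA-assigned 8 or 12 weeks for flagged gaps, beside the raw-date version.
4. Claim interval prolongation only where the two versions agree.

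On the examples above, the q8w patient who misses week 40 stays at 8 weeks and is not prolonged against a prior mean of 8.

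The cost is one derived variable and additional rows from data already captured, and possibly a slightly less favourable rate. The comparator stays on raw pre-study dates, limited to 26–86 days by eligibility. The SAP should say that this makes the DAA-based version conservative. No treatment rule changes.
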